### **8.5.2. Sulfonylurea**

The concomitant SU will be continued throughout the study at the same dose and schedule as before study entry. The SU dosage may be decreased in response to hypoglycemia.

If the patient is receiving a fixed-dose combination of metformin and an SU, the SU dosage may be decreased in response to hypoglycemia; however, the metformin dosage should remain unchanged. If a fixed-dose combination is available that would permit reduction of an SU dosage (as described above) without a change in metformin dosage, a fixed-dose combination pill can be used. If a fixed-dose combination does not meet these criteria, the metformin and SU should be administered as separate pills.

### **8.5.3. Special Treatment Considerations: Hypoglycemia**

Patients will record hypoglycemic episodes in study diaries provided by the Sponsor via the investigative sites. Patients will be encouraged to check their glucose level when signs or symptoms arise, prior to treating the event. Hypoglycemic events will be analyzed according to standard definitions of hypoglycemia.

Confirmed hypoglycemic episodes will be defined as follows in this study:

#### **Minor hypoglycemia:**

- any time a patient feels that he or she is experiencing a sign or symptom associated with hypoglycemia that is either self-treated by the patient or resolves on its own

#### **and**

- has a concurrent fingerstick blood glucose <3.0 mmol/L (54 mg/dL).

#### **Major hypoglycemia:**

- any episode with symptoms consistent with hypoglycemia resulting in loss of consciousness or seizure that shows prompt recovery in response to administration of glucagon or glucose

#### **or**

- documented hypoglycemia (blood glucose <3.0 mmol/L [54 mg/dL]) requiring the assistance of another person because of severe impairment in consciousness or behavior (whether or not symptoms of hypoglycemia are detected by the patient).

Signs and symptoms of hypoglycemia not confirmed with blood glucose values will be reported separately from confirmed episodes described above.

The patient should record the glucose meter reading, associated symptoms, and treatment in the study diary.

Events of hypoglycemia will be closely monitored. If the patient is on an SU and 1 hypoglycemic event or 2 suspected hypoglycemic events occur, the investigator should consider reducing the patient's SU dosage by approximately 50%. If additional confirmed or suspected hypoglycemic events occur, the investigator may consider additional 50% reductions of the patient's SU dosage, with discontinuation of the SU therapy as appropriate.

#### **8.5.4. Special Treatment Considerations: Laboratory Measures**

##### **8.5.4.1. Carcinoembryonic Antigen and Calcitonin**

Patients will be assessed for the tumor marker CEA and calcitonin levels at visits 3 and 11 or early discontinuation. Calcitonin levels will be measured to determine the possible effect of exenatide on thyroid c-cell function.

#### **8.6. Blinding**

This is a double-blinded study; that is, the patient, the investigator and sponsor of all 3 parties are blinded to the assigned treatment. The study also includes a single-blind placebo lead-in period where only the patients are blinded to the treatment. In addition, the Sponsor will be blinded to post-baseline measurements of the primary efficacy variable, HbA1c and antibodies to exenatide data.

Emergency unblinding for adverse events may be performed through an IVRS, which may supplement or take the place of emergency codes generated by a computer drug-labeling system. This option may be used ONLY if the patient's well being requires knowledge of the patient's treatment assignment. All calls resulting in an unblinding event are recorded and reported by the IVRS.

The investigator should make every effort to contact the Sponsor's clinical research physician prior to unblinding a patient's treatment assignment. If a patient's treatment assignment is unblinded, the Sponsor must be notified immediately by telephone.

If an investigator, site personnel performing assessments, or patient is unblinded, the patient must be discontinued from the study. In cases where there are ethical reasons to have the patient remain in the study, the investigator must obtain specific approval from the Sponsor's clinical research physician for the patient to continue in the study.

### 8.7. Concomitant Therapy

Patients will not be allowed to take any of the listed excluded medications during the treatment period ([Section 7.2](#), Exclusion Criteria).

For oral medications that are dependent on threshold concentrations for efficacy, such as antibiotics, patients should be advised to take those drugs at least 1 hour before study drug injection. If such drugs are to be administered with food, patients should be advised to take them with a meal or snack when study drug is not administered. Concomitant medications should not be taken or administered on the morning of prescheduled clinic visits.

It may be possible that due to an emergency, some patients will require treatment with insulin. If the period exceeds 10 days during a 3-month period, then the decision to keep the patient in the study should be made after consultation between the investigator and the Sponsor's clinical research physician. Each situation will be considered separately, in order to differentiate between real clinical needs and non-compliance. The decision will be documented by a note to the investigator's file.

### 8.8. Treatment Compliance

The investigator will assess the compliance of the patient at each visit based on a review of the patient's glycemic control, adherence to the visit schedule, completion of patient diaries, and any other parameters the investigator deems necessary. For patients deemed noncompliant, initial actions will include education, training, and reinforcement of the importance of compliance with the protocol. No specific study data will be collected for analysis of treatment compliance. Any deviation from the prescribed dosage regimen will be recorded in the eCRF.

A patient will be discontinued if he or she misses more than 10 consecutive days of study medication (exenatide or placebo) during the study, misses more than 10 consecutive days of oral antidiabetes therapy during the study, or if the patient's dose of metformin or SU (for reasons other than hypoglycemia) is altered for more than 10 consecutive days or 10 days in a 30-day period after study entry.

## 9. Efficacy and Safety Evaluations, Sample Collection and Testing, and Appropriateness of Measurements

Study procedures and their timing (including tolerance limits for timing) are summarized in the Study Schedule ([Attachment 1](#)).

### 9.1. Efficacy Measures

#### 9.1.1. Primary Efficacy Measure

The primary efficacy measure is the change in HbA1c from baseline to 28 weeks of treatment in adolescent patients with type 2 diabetes who are naïve to antidiabetes agents or patients who are being treated with metformin, an SU, or combination of metformin and an SU after treatment with exenatide or placebo.

#### 9.1.2. Secondary Efficacy Measures

The following secondary efficacy measures will be collected at the times shown in the Study Schedule ([Attachment 1](#)).

- proportion of patient achieving an HbA1c <7%, ≤6.5%, and <6.5%
- body weight
- FSG
- SMBG measurements before and 2 hours after the 2 main meals of the day
- fasting serum insulin concentrations
- beta-cell function and insulin sensitivity as measured by homeostasis model assessment (HOMA-B, HOMA-S) (Matthews et al. 1985)
- proportion of patients who discontinue the study due to failure to maintain glycemic control.

### 9.2. Safety Evaluations

The following safety measures will be collected at times shown in the schedule of events ([Attachment 1](#)):

- adverse events (serious and nonserious)
- incidence and frequency of hypoglycemic events
- laboratory measurements (including clinical chemistry, calcitonin, CEA and hematology and urinalysis)
- antibodies to exenatide
- ECGs
- vital signs

- pubertal assessment
- height.

Investigators are responsible for monitoring the safety of patients who have entered this study and for alerting the Sponsor or its designee to any event that seems unusual, even if this event may be considered an unanticipated benefit to the patient.

The investigator is responsible for the appropriate medical care of patients during the study.

For adverse events that are serious, or that cause the patient to discontinue before completing the study, the investigator remains responsible for following these events using an appropriate health care option. The patient should be followed until the event is resolved or explained. Frequency of follow-up evaluation is left to the discretion of the investigator.

### **9.2.1. Adverse Events**

The Sponsor has standards for reporting adverse events that are to be followed regardless of applicable regulatory requirements that may be less stringent. A clinical trial adverse event is any untoward medical event associated with the use of a drug or drug delivery system in humans, whether or not it is considered related to a drug or drug delivery system.

Lack of drug effect is not an adverse event in clinical trials because the purpose of the clinical trial is to establish drug effect.

Cases of pregnancy that occur during maternal or paternal exposures to study drug or drug delivery system should be reported. Data on fetal outcome and breast-feeding are collected for regulatory reporting and drug safety evaluation.

Study site personnel will record the occurrence and nature of each patient's pre-existing conditions, including clinically significant signs and symptoms of the disease under treatment in the study.

During the study, site personnel will record any change in the condition(s) and the occurrence and nature of any adverse events.

After the informed consent and assent documents are signed, all adverse events related to protocol procedures are reported to the Sponsor or its designee via eCRF.

**All** adverse events occurring after the patient receives the first dose of study drug must be reported to the Sponsor or its designee via eCRF.

Study site personnel will record any daily dosage that exceeds the maximum dosage in the protocol or in the relevant reference safety document (for example, clinical dosage section for humans in the Investigator Brochure); whichever is greater, via eCRF.

Investigators will be instructed to report to the Sponsor or its designee their assessment of the potential relatedness of each adverse event to protocol procedure, study drug, and/or injection pen via eCRF.

Study site personnel must alert the Sponsor or its designee within 24 hours of the investigator **unblinding** a patient's treatment arm assignment for any reason.

If a patient's dosage is reduced or treatment is discontinued as a result of an adverse event, study site personnel must clearly report to the Sponsor or its designee via eCRF the circumstances and data leading to any such dosage reduction or discontinuation of treatment.

Any clinically significant labs or vital sign measurements that result in a diagnosis should be reported to the Sponsor or its designee using the "Adverse Events/Pre-existing Condition" page of the eCRF. In cases where the investigator notices an unanticipated benefit to the patient, study site personnel should report "unexpected benefit" with the actual event term to the Sponsor or its designee via eCRF (for example, the complete actual term would be "unexpected benefit—sleeping longer").

#### **9.2.1.1. Serious Adverse Events**

Serious adverse event collection begins after the patient has signed informed consent and has received study drug. If a patient experiences a serious adverse event after signing informed consent, but prior to receiving study drug, the event will NOT be collected unless the investigator feels the event may have been caused by a protocol procedure.

Study site personnel must alert the Sponsor or its designee of any serious adverse event within 24 hours of investigator awareness of the event via a Sponsor-approved method. Alerts issued via telephone are to be immediately followed with official notification on study-specific serious adverse event forms. A serious adverse event is any adverse event from this study that results in one of the following outcomes:

- death
- initial or prolonged inpatient hospitalization
- a life-threatening experience (that is, immediate risk of dying)
- persistent or significant disability/incapacity
- congenital anomaly/birth defect
- considered significant by the investigator for any other reason.

Important medical events that may not result in death, be life-threatening, or require hospitalization may be considered serious adverse drug events when, based upon appropriate medical judgment, they may jeopardize the patient and may require medical or surgical intervention to prevent one of the outcomes listed in this definition.

The Sponsor or its designee will be alerted to a study-specific outcome as a serious adverse event only if the investigator deems it to be related to use of the study drug or injection pen or by a protocol procedure.

When a condition related to the injection pen necessitates medical or surgical intervention to preclude either permanent impairment of a body function or permanent damage to a body structure, the serious outcome of "required intervention" will be assigned.

Serious adverse events occurring within 30 days after the last dose of study drug will be collected, regardless of the investigator's opinion of causation. Thereafter, serious adverse events are not required to be reported unless the investigator feels the events were related to either study drug, drug delivery system, or a protocol procedure. For information on the collection of serious adverse events during the safety follow-up period, please see Protocol Addendum 4.

### **9.2.2. Other Safety Measures**

Twelve-lead ECGs will be obtained according to the Study Schedule ([Attachment 1](#)). ECGs are to be performed locally.

The ECGs will be interpreted by a qualified physician (the investigator or qualified designee) at the site as soon as possible after the time of ECG collection, and ideally while the patient is still present, for immediate patient management and to determine whether the patient meets entry criteria. If a clinically significant increase in the QTc interval from baseline is present, then the investigator should assess the patient for symptoms (such as palpitations, near syncope, syncope). The physician must document his/her review of each ECG.

Patients will record hypoglycemic episodes in study diaries provided by the Sponsor via investigative sites. Patients will be encouraged to check their glucose level when signs or symptoms arise (as described in [Section 8.5.3](#)) before treating the event and record the glucose meter reading, associated symptoms, and treatment in the study diary.

Pubertal assessment will be summarized based on Tanner Scale.

### **9.2.3. Safety Monitoring**

The Sponsor's clinical research physician or scientist will monitor safety data throughout the course of the study.

The Sponsor's clinical research physician or scientist will review serious adverse events within time frames mandated by company procedures and will review trends, laboratory analytes, and adverse events at periodic intervals.

In the event that safety monitoring uncovers an issue that needs to be addressed by unblinding at the group level, only members of the data monitoring committee (DMC); (a group created to advise the Sponsor regarding the continuing safety of study participants and the continuing validity and scientific merit of the trial) can conduct additional analyses of the safety data.

### **9.2.4. Complaint Handling**

The Sponsor collects product complaints on study drugs and drug delivery systems used in clinical trials in order to ensure the safety of study participants, monitor quality, and to facilitate process and product improvements.

Complaints related to unblinded comparator drugs or concomitant drugs/drug delivery systems are reported directly to the manufacturers of those drugs/devices in accordance with the package insert.

For blinded studies, all product complaints associated with material packaged, labeled, and released by the Sponsor will be reported via product complaint forms.

The investigator or his/her designee is responsible for handling the following aspects of the product complaint process in accordance with the instructions provided for this study:

- recording a complete description of the product complaint reported and any associated adverse events using the study-specific complaint forms provided for this purpose
- faxing the completed product complaint form within 24 hours to the Sponsor or its designee
- determining when a drug/drug delivery system is to be returned for investigation.

If the investigator believes that an adverse event is related to the drug delivery system, but the patient has not communicated a complaint, the investigator should assume a complaint and report the product complaint to the Sponsor or its designee within 24 hours.

### **9.3. Sample Collection and Testing**

[Attachment 2](#) lists the specific tests performed for this study.

#### **9.3.1. Samples for Standard Laboratory Testing**

Blood samples will be collected at the times specified in the Study Schedule ([Attachment 1](#)). Standard clinical laboratory tests, including chemistry, hematology, and urinalysis panels will be performed and analyzed by a central laboratory. A urine pregnancy test will be performed locally at all clinic visits for females of childbearing potential. If the urine pregnancy test at any clinic visit is positive, a serum pregnancy test will be performed centrally to confirm the result.

Laboratory analyte results that could unblind the study will not be reported to investigative sites or other blinded personnel until the study has been unblinded.

Investigators must document their review of each laboratory report.

Samples collected for specified laboratory tests will be destroyed within 60 days of receipt of confirmed test results. Certain samples may be retained for a longer period, if necessary, to comply with applicable laws, regulations, or laboratory certification standards.

#### **9.3.2. Stored Samples**

At Visits 3 and 11, or if the patient exits the study early (after Visit 3 but prior to Visit 11), blood samples will be drawn and the serum and plasma will be stored and may be used for future testing to support investigation of the primary and secondary endpoints of the study or for other markers of metabolic or cardiovascular interest. A sponsor-designated referral laboratory will perform any testing of the stored samples. Results of stored sample testing will not be reported to investigative sites.

Stored samples will retain the patient identifier (for example, trial patient numbers) and, therefore, will not be stored indefinitely. Samples will be stored at a Sponsor designated site for

a maximum of 3 years after last patient visit for the study; any sample remaining at that time will be destroyed.

### **9.3.3. Collection Procedures**

Blood (sampled by venipuncture) and urine will be collected from patients during the course of the study. All lab specimens will be collected at the times specified in Study Schedule ([Attachment 1](#)).

## **9.4. Appropriateness of Measurements**

All efficacy assessments included in this study are generally regarded as reliable and accurate assessments of diabetes control. Safety assessments will be consistent with good clinical practice (GCP) guidelines.

## 10. Data Quality Assurance

To ensure accurate, complete, and reliable data, the Sponsor or its representatives will do the following:

- provide instructional material to the study sites, as appropriate
- conduct a start-up training session to instruct the investigators and study coordinators. This session will give instruction on the protocol, the completion of the eCRFs, and study procedures
- make periodic visits to the study site
- be available for consultation and stay in contact with the study site personnel by mail, telephone, and/or fax
- review and evaluate eCRF data and use standard computer edits to detect errors in data collection
- conduct a quality review of the database.

In addition, the Sponsor or its representatives may periodically check a sample of the patient data recorded against source documents at the study site. The study may be audited by Amylin or its representatives, and/or regulatory agencies at any time. Investigators will be given notice before an audit occurs.

To ensure the safety of participants in the study, and to ensure accurate, complete, and reliable data, the investigator will keep records of laboratory tests, clinical notes, and patient medical records in the patient files as original source documents for the study. If requested, the investigator will provide the Sponsor, applicable regulatory agencies, and applicable ethical review boards (ERBs) with direct access to original source documents.

### 10.1. Direct Data Entry and Computerized Systems

An electronic data capture system will be used in this trial. Some or all of a patient's data (for example, a rating scale, daily dosing schedule, patient diary, event diary) may be directly entered into the system on an eCRF (for example, personal desk assistant or by means of IVRS) at the time that the information is obtained. In these instances where there is no prior written or electronic record of the data, the eCRF (for example, personal desk assistant, or by means of IVRS) will serve as the source document.

Electronic case report form data will be encoded and stored in a clinical trial database.

Any data for which the eCRF will serve as the source document will be identified and documented by each site in that site's study file.

Data from complaint forms submitted to the Sponsor will be encoded and stored in the global product complaint management system.

## 11. Sample Size and Statistical Methods

### 11.1. Determination of Sample Size

Approximately 195 patients diagnosed with type 2 diabetes will participate in this study. Approximately 65 patients will be randomized to receive placebo and 130 patients will be randomized to receive exenatide (65 per exenatide treatment arm). A sample of 65 patients per treatment arm would provide >95% power to reject the null hypothesis of no difference among treatments assuming true mean changes in HbA1c of -0.7, -0.5, and 0 for patients receiving exenatide 10 µg twice daily, exenatide 5 µg twice daily, and placebo twice daily, respectively (based on results of previous Studies 2993-112, CCI ██████████, H8O-MC-GWAA, H8O-MC-GWAD). This power computation also assumes a common standard deviation of 1.0% and a two-sided significance level of 0.05. Assuming the same true mean changes in HbA1c, common standard deviation, and two-sided significance level, 65 patients per treatment arm would also provide >95% power to detect a difference between 10 µg exenatide twice daily and placebo treatments, and 80% power to detect a difference between 5 µg exenatide twice daily and placebo with a Fisher Protected Testing procedure (Hayter 1986).

Due to an approximate 23% discontinuation rate in the exenatide arms (based on results from 2993-112), 65 patients randomized per treatment arm will be sufficient to observe 50 completers per treatment arm.

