## 7. Study Population

A sufficient number of individuals will be screened to enroll at least 195 patients (65 per treatment arm). This number is deemed sufficient to allow for approximately 50 subjects per treatment arm to complete treatment.

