1.3 Number of patients

Approximately 195 patients diagnosed with type 2 diabetes were planned to be enrolled. Approximately 65 patients were to be randomized to receive placebo and 130 patients were to be randomized to receive exenatide (65 per exenatide treatment arm). A sample of 65 patients per treatment arm would provide >95% power to reject the null hypothesis of no difference among treatments assuming true mean changes in HbA1c of -0.7, -0.5, and 0 for patients receiving exenatide 10 µg twice daily, exenatide 5 µg twice daily, and placebo twice daily, respectively (based on results of previous Studies 2993-112, CCI, H8O-MC-GWAA, H8O-MC-GWAD). This power computation also assumes a common standard deviation of 1.0% and a two-sided significance level of 0.05. Assuming the same true mean changes in HbA1c, common standard deviation, and two-sided significance level, 65 patients per treatment arm would also provide >95% power to detect a difference between 10 µg exenatide twice daily and placebo

treatments, and 80% power to detect a difference between 5 µg exenatide twice daily and placebo with a Fisher Protected Testing procedure (Hayter 1986).

Due to an approximate 23% discontinuation rate in the exenatide arms (based on results from 2993-112), 65 patients randomized per treatment arm would be enough to observe 50 completers per treatment arm. Patients will be eligible to participate if they are not achieving adequate glycemic control (i.e. HbA1c at screening is 6.5% to 10.5%, inclusive) with metformin, an SU, or metformin and an SU, or diet and exercise only. Patients will be stratified to treatment assignment based on diabetes therapy at enrolment and screening HbA1c. The three-arm design was intended to allow comparison of exenatide at doses of 5 µg twice daily and 10 µg twice daily with placebo twice daily.

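### The planned power figures (>95%, >95%, 80%) assume no loss of Week 28 data, although the same section expects 50 of 65 patients per arm to complete; the 80% for 5 µg has no margin to absorb that loss

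*Protocol*

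**What the plan says.** Protocol 11.1 attaches its power statements to 65 patients per arm. For the overall test: "A sample of 65 patients per treatment arm would provide >95% power to reject the null hypothesis of no difference among treatments". For the higher dose: "65 patients per treatment arm would also provide >95% power to detect a difference between 10 µg exenatide twice daily and placebo treatments". For the lower dose: "80% power to detect a difference between 5 µg exenatide twice daily and placebo with a Fisher Protected Testing procedure". The inputs are "assuming true mean changes in HbA1c of -0.7, -0.5, and 0 for patients receiving exenatide 10 µg twice daily" (then 5 µg and placebo, in that order) and "a common standard deviation of 1.0% and a two-sided significance level of 0.05".

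The following paragraph takes a discontinuation rate of about 23%, observed in the exenatide arms of an earlier study, and concludes that "65 patients randomized per treatment arm will be sufficient to observe 50 completers per treatment arm". Protocol 7 says the same of the enrolment target: "This number is deemed sufficient to allow for approximately 50 subjects per treatment arm to complete treatment".

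SAP 1.3 repeats the powers and the completer count ("65 patients randomized per treatment arm would be enough to observe 50 completers per treatment arm"). It then reports that recruitment stopped at 122 randomized and that the two doses are pooled, with about 87% power. For that pooled figure alone, it says that discontinuation was not taken into account.

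Protocol 11.2.6 makes the primary analysis an MMRM on all post-baseline HbA1c values, with inference on the Week 28 difference. An early-termination value taken off schedule is moved to the following planned visit; SAP 4.2.4.2 has a similar rule.

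**The concern.** The section sets two sample sizes side by side, 65 randomized and 50 completing, without saying which one the powers describe. A reader who sees a dropout paragraph directly after a power paragraph will normally take it that 65 already includes the allowance. It does not: 65 is both the number used for power and the number randomized. SAP 1.3 strengthens that impression, because it qualifies the later pooled figure for discontinuation and leaves the earlier three unqualified.

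At stake is how the 5 µg comparison is described. A printed power of 80% means a 20% chance of missing a true 0.5-point effect. With any appreciable loss of Week 28 information, the chance is larger.

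**Working it through.** **Inputs** (protocol 11.1): mean changes −0.7, −0.5 and 0; SD 1.0; two-sided 0.05; 65 per arm; 23% discontinuation. Allocation is 2:2:1:1 (protocol 6.1.3), which is 1:1:1 once the two placebo volumes are pooled. The SD is taken as the residual SD, since no covariate-adjusted value is given.

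**Formulas**
- Overall test: non-central F with 2 and 3n − 3 df and λ = n × Σ(μᵢ − μ̄)²/σ². Here μ̄ = −0.4, so the sum is 0.09 + 0.01 + 0.16 = 0.26. λ is 16.9 at n = 65 and 13.0 at n = 50.
- Pairwise, unprotected: power ≈ Φ(δ√(n/2)/σ − 1.96).
- Fisher protected: simulated probability that the F-test and the pairwise t-test are both significant at 0.05.

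**Reproducing the plan, n = 65.** For 5 µg, 0.5 × √32.5 = 2.850; 2.850 − 1.96 = 0.890; Φ = 81.3% unprotected.

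**At the plan's completer count.** 65 × 0.77 = 50.05, so n = 50. For 5 µg, 0.5 × √25 = 2.5; 2.5 − 1.96 = 0.54; Φ = 70.5% unprotected.

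| | Stated | n = 65 | n = 50 |
|---|---|---|---|
| Overall F | >95% | 96.3% | 90.2% |
| 10 µg, protected | >95% | 95.9% | 89.1% |
| 5 µg, protected | 80% | 80.4% | 68.7% |
| At least one dose, protected | not stated | 96% | 90% |

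**Margin.** The smallest number of analysable patients per arm that keeps each stated figure is 61 for the overall test, about 62-63 for 10 µg (protected; 54 unprotected) and about 65 for 5 µg (protected).

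**What the MMRM recovers.** The Week 28 information is I = Σ cₖ Rₖ⁻¹, where cₖ patients have their first k of the four post-baseline visits and Rₖ is the correlation matrix of those visits. The effective n is 1/[I⁻¹]₄₄. Assumptions not in the documents: 15 dropouts per arm spread evenly over the four visit intervals, and compound-symmetric or AR(1) correlation ρ.

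| Early-discontinuation HbA1c | ρ | Effective n | 5 µg, protected |
|---|---|---|---|
| None used | 0.5 | 51-53 | 70-72% |
| None used | 0.7 | 53-56 | 71-74% |
| None used | 0.9 | 57-59 | 75-76% |
| Every dropout, moved to next planned visit | 0.7 | 57-60 | 75-77% |
| Every dropout, moved to next planned visit | 0.5-0.9 | 55-63 | 73-79% |

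In the most favourable case (ρ = 0.9, full early-discontinuation data, effective n about 61-63), the overall test is at about 95-96% and 10 µg at about 95%. The 5 µg figure stays below 80% in every row.

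**The trial as run.** 122/3 = 40.7 per arm. Unprotected 5 µg power is Φ(0.5 × √20.33 − 1.96) = Φ(0.295) = 61.6%. With Fisher protection it is about 59%. Both assume no dropout.

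**The case against.** **There is no arithmetic error.** The powers are stated for 65 per arm and are right at 65. The completer count is a separate, correct sentence. This stands: the defect is an unstated assumption. A reader might infer that the sponsor miscalculated, and the documents do not support that.

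**69% is not the power of the primary analysis.** It describes a completers-only comparison, whereas the plan uses an MMRM with partial data and relocated early-termination values. This stands too, so 69% is only a lower bound. With ρ = 0.7 and full early-discontinuation data, the shortfall is about 3-5 points rather than 11.

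**Not all three figures must fail.** A reader might infer that every printed power is overstated. At 50 completers they are. Under the most favourable MMRM assumptions, the overall and 10 µg figures hold at about 95%.

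**The 5 µg comparison is not the success criterion.** Protocol 5.1 requires superiority for at least one dose, and power for that is still about 90% at 50 completers. The point therefore does not show that the original design was underpowered for its primary objective.

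**The 23% was observed in exenatide arms only.** True, but the plan itself applies 50 completers to every arm. If placebo kept all 65, unprotected 5 µg power would be Φ(0.5/√(1/50 + 1/65) − 1.96) = Φ(0.698), about 76%, or about 75% protected. That is still short of 80%.

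**The design was superseded.** SAP 1.3 stops at 122 and pools the doses, and SAP 6 no longer requires the Fisher procedure. This limits the practical weight. A reader might still use the per-dose powers to interpret a null 5 µg result in the dose-level sensitivity analysis (SAP 4.2.4.3). They cannot serve for that, with or without a dropout correction, because they describe 65 or 50 per arm and the trial has about 41.

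**Conclusion.** The concern holds as a missing qualification. The figures in protocol 11.1 and SAP 1.3 are no-dropout figures printed beside a 23% dropout expectation. The 5 µg figure is the one that fails throughout: 80% as printed, about 70-79% for the planned MMRM and about 69% as the completers-only lower bound. The overall and 10 µg figures drop to about 90% and 89% at 50 completers but may hold near 95% with high visit correlation and full early-discontinuation data.

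The 90%, 89% and 69% values use only the plan's inputs, including 50 completers in every arm and SD 1.0 as the residual SD. The MMRM range also needs correlations of 0.5-0.9, a dropout pattern and early-discontinuation attendance, all of them assumed here. It further supposes that dropout costs information without shrinking the treatment effect.

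The documents do not support going on to conclude that more patients should have been randomized. They nowhere promise 80% after dropout, and recruitment has ended.

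**What to change.** - **Protocol 11.1 and SAP 1.3:** state that >95%, >95% and 80% assume no missing Week 28 data, as SAP 1.3 already does for the pooled figure. Add about 90%, 89% and 69% at 50 completers per arm, labelled as the completers-only lower bound. Add an MMRM-based range with its correlation, dropout-timing and early-discontinuation assumptions written out.
- **SAP 1.3 only:** note that the per-dose powers do not apply to the 122 patients randomized (about 41 per arm; 5 µg about 59% with no dropout), and that the dose-level sensitivity analysis should not be read against them.

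The cost is wording. Enrolment, design and analysis stay as they are; the stated power becomes less favourable.
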